10.2. Descriptive analysis

After data quality check, we prepare data description tables including number of observations, mean and standard deviation of variables. We will use graphical methods (e.g. scatterplots) to get insight in the correlation between different exposure variables and the associations between specific exposures and health endpoints as well.

10.3. Statistical modelling

We will use mixed effect regression model to estimate the effects of different pollutant sources (tailpipe or non-tailpipe) on the change in health point, which will be defined by difference of various factors such as FEV1 and FVC between pre-exposure and post-exposure (0, 2, or 18 hours). For each endpoint, one key time post-exposure has been selected, based on the time of maximal effect in previous controlled exposure studies, for example for FEV1 this is 2 hours post exposure.²³ In this model, when measurements and pollutant characterization become available, the exposure covariates will be the integrated average concentration of the various pollutants and /or sources during the exposure period. We will take the results of the source apportionment and feed them into the model. The method will provide estimates of exposure due to tailpipe emissions (Black Carbon and Organic Aerosol) and non-tailpipe, specifically break wear and tyre & road wear, emissions. We will include these exposure types in the model. We will start with a single-exposure covariate models (for every source type), then we can decide how to develop a model with all of the significant source types. Levels (eg. Integrated average concentration) of each source (tailpipe/non-tailpipe) will be included in the model. The effects of different pollutants will be compared based upon statistical significance and the effect size for selected exposure contrasts, such as a pre-defined change of the concentration of the pollutant or interquartile range. Two pollutant models will be specified as well to evaluate which pollutant has the strongest association with a certain health endpoint.

In our models we will account for potential confounders which may be present as the exposure contrast cannot be entirely predicted by the design: we will include meteorological variables such as temperature, relative humidity and wind direction during the exposure time; as well as individual characteristics such as age, gender, severity of asthma and allergies.

We will use R (version 4.1.3 or newer; R Development Core team) for the application of mixed models using functions from the lme4 and nlme packages.

11. Ethics

The study will be sponsored and managed by QMUL and supported by Imperial College London, according to MRC guidance:

<https://www.mrc.ac.uk/publications/browse/good-research-practice-principles-and-guidelines/>

This study has received University Research Ethics Committee approval (QMERC22.170.). The study will be carried out according to the principles of the Helsinki Agreement.

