6.3. Primary endpoint

- Lung function as measured by Forced Expiratory Volume in one second (FEV1)

Secondary endpoint

- Spirometry (FVC, FVC/FEV1 ratio, z Scores)
- Fractional Expired Nitric Oxide (FeNO)
- Peak expiratory flow
- Oscillometry
- Asthma symptoms
- Asthma control Test
- Quality of Life: AQLQ
- Immune responses: damage-associated molecular patterns (DAMPs) and alarmins, such as high mobility group box 1 (HMGB1) S100 proteins, myeloperoxidase-DNA complexes (MPO-DNA), IL-33, Th2 and Th17 cytokines and metal deposition in the nasal airways

Control variables

- Estimated VO2max
- Heart rate
- Air quality measured as: PM10 and PM2.5, particle number concentration (PNC) and gaseous pollutants ozone (O3), nitrogen dioxide (NO2), black carbon.
- Pollen count
- Temperature and humidity
- Physical activity (accelerometry)
- Personal air quality (Plume labs)

Biobanking

- Venous blood
- Nasal Mucus
- Urine

Banking

- PM filters

7. Study population

Asthma is a complex disease now recognized to include multiple phenotypes. Therefore, to ensure maximum generalisability of our findings, we will recruit participants with the most common phenotype: allergic asthma that started in childhood/adolescence. We will exclude those with a BMI >30 to exclude obese, steroid-resistant phenotypes. Participants (male and female) recruited to the study will be over 18 years old with mild to moderate stable asthma. We will exclude those

hospitalized with an asthma attack in the last 12 months, and those with more than three episodes requiring oral corticosteroids in the last 12 months. To reduce the impact of confounders participants must neither smoke, nor live with current smokers, must live within greater London, and have no occupational exposure to PM or oxidant gases.

With input and guidance from our active patient and public involvement group at the Asthma UK Centre for Applied Research (AUKCAR), participants will be recruited from primary care.

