9.7. Randomization

The study will use a 6X3 Williams crossover inequality test of paired differences.¹⁷ as such the participants will be randomised to a sequence for their exposures to the three sites. Six sequences will be used (ABC/ BCA/ CBA/ ACB/ BAC/ CAB).

9.8. Health effects assessment on exposure visit days:

Participant flow through an exposure session is summarised in figure 2, while participant flow through the study is summarised in figure 3. On the morning of the site visits participants will first provide a urine sample while at home (9:00 am) Participants will be provided with a taxi to the study site. The participants will be transported taxi with closed windows and air circulation enabled, to the exposure sites.

Once at the exposure sites (10:00am-11:00am) baseline spirometry and determination of FeNO and sample collection (4x10 ml blood collection and baseline nasal lavage) will be performed at the field laboratory. At this time a brief health questionnaire will be administered to assess recent asthma control and ensure the volunteer is free of respiratory infection and has not experienced a recent exacerbation of their asthma.

During the two and a half hour exposure and exercise protocol (11:00am-13:30 pm), participants' heart rate will be monitored throughout the exposure period; at the half way point, after sufficient recovery (12:15am) participants will perform spirometry FeNO and Oscillometry. Immediately post-exposure the participants will perform spirometry, oscillometry FeNO and mucus sample collection at the field lab. The following day, volunteers will return for 28-hour post measurements; biosamples, spirometry and FeNO.

IONA: Schedule of assessment and exposure								
	Pre-Study	Screening	3 day pre	Pre	Exposure	Post	24 hour post	3 days post
		Phys lab	Self assess	Field lab	Field lab	Field lab	Phys lab	Self assess
Consent	x							
Exercise test		x						
FeNO		x		x	x	x	x	
Oscillometry		x		x	x	x	x	
Spirometry		x		x	x	x	x	
Asthma control test		x						
QOL: AQLQ		x						
Baseline questionnaire		x						
Daily Symptom Q		x	x	x		x	x	x
PEF Test			x				x	
Personal air quality			x					
Physical activity			x					
Venepuncture				x			x	
Nasal lavage				x		x	x	
Urine sample				x			x	
Heart rate					x			

Figure 2. Flow of participants through IONA study days

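### FEV1 is analysed as a raw pre-to-post change without naming the same-visit pre-exposure FEV1 as a covariate, which may give up some precision at no saving in data

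*Protocol*

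**What the plan says.** The primary endpoint in Protocol section 6.3 is FEV1. Section 10.3 sets the response in the mixed models as the "difference of various factors such as FEV1 and FVC between pre-exposure and post-exposure", with one key time chosen per endpoint ("for example for FEV1 this is 2 hours post exposure").

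For adjustment, section 10.3 says "we will include meteorological variables such as temperature, relative humidity and wind direction during the exposure time", and then "as well as individual characteristics such as age, gender, severity of asthma and allergies". Pre-exposure FEV1 is not named in either list, and no other section adds it.

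The value is available. Section 9.8 places it before each exposure session: "Once at the exposure sites (10:00am-11:00am) baseline spirometry and determination of FeNO". The schedule of assessments in that section also shows spirometry, FeNO and oscillometry at the pre-exposure time.

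Section 10.1 powers the trial on the same change scale, as the difference in FEV1 reduction between two sites.

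**The concern.** A change score fixes the slope on the pre-exposure value at 1. If that day's reading carries short-term variation that does not persist to the post-exposure reading, subtracting it in full adds noise to the outcome. Estimating the slope removes that excess.

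In a three-period crossover, the site contrasts come mainly from comparisons within a participant. A visit-level covariate measured before exposure can sharpen those comparisons, and pre-exposure FEV1 is the natural candidate. What is at stake is the width of the confidence intervals for the site contrasts. Spare precision has some value here, because section 10.1 itself says that the exposures to be contrasted are not yet settled.

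**Working it through.** **Inputs.** From Protocol section 10.1: difference 4.69, SD 6.4, 30 participants (5 per sequence, 6 sequences), significance level 0.05, power 91.54%. The unit of 4.69 and 6.4 is not stated. Assumed: r, the within-person, same-visit correlation of pre- and post-exposure FEV1, and equal pre and post variances.

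**1. The plan's own figure.** Treat 6.4 as the SD of the paired difference in change.
- Noncentrality = 4.69 / (6.4/√30) = 4.014.
- Degrees of freedom = 30 − 6 = 24.
- Two-sided alpha = 0.05/3, for three site pairs.
- Power from the noncentral t distribution = 0.9154.

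This matches 91.54%. The division by 3 is inferred from the match, since section 10.1 states only 0.05.

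**2. Variance ratio.** Let σ² be the within-person variance of a single reading.
- Raw change: variance 2σ²(1 − r).
- Adjusted for the pre-exposure value: residual variance σ²(1 − r²).
- Ratio: (1 − r²) / [2(1 − r)] = (1 + r)/2.

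**3. Power by the formula at n = 30.** The effective SD is 6.4 × √[(1+r)/2]. One degree of freedom is spent on the slope, so df = 23.

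| r (assumed) | Variance ratio | Effective SD | Power |
|---|---|---|---|
| raw change, df 24 | 1 | 6.40 | 91.5% |
| 0.5 | 0.75 | 5.54 | 97.4% |
| 0.7 | 0.85 | 5.90 | 95.4% |
| 0.9 | 0.95 | 6.24 | 92.8% |

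In terms of sample size, 30 × (1+r)/2 gives 22.5, 25.5 and 28.5. So about 23, 26 and 29 participants would match the precision of 30 on raw change.

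**4. Cost of estimating the slope.** The formula treats the slope as known. Simulating the six-sequence, three-period design with 30 participants gives ratios of about 0.77, 0.87 and 0.98 at r = 0.5, 0.7 and 0.9, and essentially no gain at r = 0.95. With these ratios, SD = 6.4 × √ratio is 5.62, 5.97 and 6.34, and power at df 23 is about 97.0%, 94.9% and 92.0%. The powers in step 3 are therefore slightly optimistic.

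**5. Form of the covariate.** In a random-intercept model, the raw same-visit value mixes differences between people with deviations between visits. Simulated with a between-participant SD of 15 and r from 0.3 to 0.9, the raw value gave variance ratios of 0.89 to 0.98 in the less extreme setting (participants also differing in response, SD 4) and 0.95 to 0.98 without such differences. With the participant mean and the visit deviation entered separately, the ratios were 0.67 to 0.98. The split is needed to recover most of the gain.

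**The case against.** The strongest reply is that nothing here is wrong. The change score is a valid outcome, the trial is powered on the same scale, and the stated power is correct for it. Both covariate lists are introduced as examples, so a separate SAP could add the pre-exposure value without contradicting the protocol. All of this stands. The point concerns only what section 10.3 fixes and names.

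The trial also has some slack on its own assumptions. With 20 to 30% dropout, 48 × 0.80 = 38.4 and 48 × 0.70 = 33.6, so about 33 to 38 participants complete. Raw-change power at those numbers is about 94% to 97%. This stands too, and it limits the practical importance.

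The size is assumed. If r is very high there is nothing to gain. If 4.69 and 6.4 are percentage changes, the outcome is already scaled to the pre-exposure value and (1+r)/2 does not apply directly.

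Three stronger readings are tempting, and the protocol does not support them:
- A reader might infer that chance differences in pre-exposure FEV1 bias the site contrasts. The order of sites is randomised, so such differences add variance, which the standard error already reflects.
- A reader might infer that age, gender, severity and allergies are useless covariates in a crossover. Section 10.3 lists them as potential confounders, not for precision. With incomplete visits and measured concentrations as exposure, some between-person information enters the model, and there they can matter.
- A reader might apply the power gains to the pollutant-source models of section 10.3. The figures are for the pairwise site contrast of section 10.1. Daily concentrations are not randomised, so adjusted and unadjusted models need not estimate the same quantity there.

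**Conclusion.** The point holds as an efficiency recommendation. Section 10.3 settles on a raw change and does not name the one visit-level baseline that is measured every time.

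For the randomised site contrasts the likely benefit is a variance reduction of about 23% at r = 0.5, 13% at r = 0.7 and 2% at r = 0.9, vanishing from about r = 0.95. This rests on an assumed r, equal pre and post variances, and FEV1 analysed on an unscaled basis. The direction is secure across the plausible range short of very high r; the size is not. The r that matters is the correlation left after differences between participants are removed, so a high FEV1 correlation across people does not by itself show that the gain is negligible.

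**What to change.** In section 10.3, state that the FEV1 site comparison models post-exposure FEV1 (or the change, which gives the same site contrasts once the pre-exposure value is in the model) with the same-visit pre-exposure FEV1 as a covariate. Enter it as two terms: the participant's mean pre-exposure value and the visit's deviation from that mean. Apply the same form to the other endpoints measured before exposure, such as FVC, FeNO and oscillometry.

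For the source-concentration models, report both the baseline-adjusted and the unadjusted change results, and say that they may answer different questions.

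The cost is a sentence or two and one or two degrees of freedom. No new data are needed and the sample size need not change. The downside is that the gain may be negligible if r is very high. The wording should be fixed before outcome data are examined.

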Inclusion and exclusion criteria	
Inclusion criteria:
 
 • Doctor diagnosed asthma starting on or before age 16 years • Prescribed regular inhaled corticosteroid medication • Able to use a static exercise bicycle for the study duration 
Exclusion criteria:
 
 • Tobacco smoking, or living with smoker • Body mass index (BMI) > 30 • Asthma hospitalisation within 12 months • Three or more asthma episodes requiring oral corticosteroid medication within 12 months • Other major lung disease • Chest surgery within 6 months • Unable to give informed consent • Occupational exposure to particulate matter (PM) or high levels of air pollution
Statistical methodology and analysis (if applicable)	Mixed effects models, taking into account repeated measurements within participants.
Study duration	01/08/2022- 1/12/2024

5. Introduction

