6.1. Primary objective

Objective 1: Assess and compare the acute health effects: changes in lung function and airway inflammation, in mild/moderate asthmatics exposed at three selected microenvironments with contrasting traffic profiles to increase contrast in particulates from brake wear, tyre wear, and road abrasion.

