6.2. Secondary objective

Objective 2: Provision of an air pollutant database (PM_{2.5} and PM₁₀ mass and chemical composition, PNC and NO₂) and a time series of source apportioned PM_{2.5} and PM₁₀ covering all exposure days at the three selected sites.

Objective 3: Examine the relationship between variations in daily non-tailpipe source fractions derived from tire, brake and road wear, with the deposited dose determined in the nasal airways and the physiologic and immunologic responses observed.

Objective 4: Provision of a biobank of plasma and nasal mucus samples for future work examining molecular signature of exposure and response.

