10.1. Sample size

Since we will randomize the participants to assign a sequence for their exposures to the three sites we will have six sequences (ABC/ BCA/ CBA/ ACB/ BAC/ CAB), a 6X3 Williams crossover inequality test of paired differences.¹⁷ For a significance level of 0.05, a Δ (Difference between the reduction in FEV1 between 2 sites) of 4.69 with a standard deviation of 6.4²³ and a total of 30 participants (5 per sequence) we have a power of 91.54%. However, assuming a dropout rate of 20 to 30% and taking into account that specific exposures to contrast are not available yet and will be assessed when the exposure methods are developed, we intend to recruit 48 participants in total. We will define 12 groups of 4 individuals and then assign a group to each participants. Each two groups will have a same sequence.

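### Section 10.3 writes out only concentration models, so the randomised and powered between-site FEV1 comparison has no stated model; and the 91.54% power in 10.1 does not follow from a two-sided 0.05 per comparison

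*Protocol*

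**What the plan says.** **Objective.** Section 6.1 sets the primary objective: "Assess and compare the acute health effects: changes in lung function and airway inflammation, in mild/moderate asthmatics exposed at three selected microenvironments". Section 6.3 makes FEV1 the primary endpoint. Section 6.2 lists a separate Objective 3: "Examine the relationship between variations in daily non-tailpipe source fractions derived from tire, brake and road wear", in relation to nasal dose and the observed responses.

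**Design and power.** Participants are randomised to one of six site sequences. Section 9.7 says: "The study will use a 6X3 Williams crossover inequality test of paired differences". Section 10.1 repeats this test and defines its effect as the "Difference between the reduction in FEV1 between 2 sites", set at 4.69 with a standard deviation of 6.4. The power statement begins "For a significance level of 0.05" and reports "a total of 30 participants (5 per sequence) we have a power of 91.54"%. The recruitment target is 48, to cover 20 to 30% dropout, with participants placed in 12 groups of four.

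**Analysis.** The synopsis says only "Mixed effects models, taking into account repeated measurements within participants". Section 10.2 is descriptive. Section 10.3 gives its aim as estimating the effects of tailpipe and non-tailpipe sources on the pre-to-post change. It specifies that "the exposure covariates will be the integrated average concentration of the various pollutants and /or sources during the exposure period". It then lists single-source, multi-source and two-pollutant models, adjusted for weather and participant characteristics. Site appears neither among the exposure terms nor among the adjustment terms.

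**Another mention of site.** Section 14.3 says that immune and physiologic responses will be examined by site classification, as well as by ambient metals and nasal dose. It gives no model or test.

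**The concern.** Randomisation of sequence protects the comparison between sites. It does not protect the comparison between high-concentration and low-concentration days, and 10.3 itself accepts that confounders may be present because the design does not fully determine the exposure contrast. If 10.3 is followed as written, the output is a set of slopes on measured concentrations. The site difference on which the trial was sized is not among the quantities that the section describes.

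The second issue concerns error control. Three sites give three pairs. Section 10.1 quotes one alpha and does not say whether it applies to each pair or to all three together. The power figure should settle this, but it does not agree with 0.05 used per pair. Under the per-pair reading, the chance of at least one false positive could reach 3 × 0.05 = 0.15 (the upper bound). Under the other reading it is held at 0.05. Whoever writes the site analysis needs to know which is meant.

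**Working it through.** **1. Where each analysis is stated**

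| Section | Quantity compared | Model or test |
|---|---|---|
| 6.1 (Objective 1) | Responses at three sites | None given |
| 9.7, 10.1 | Paired difference in FEV1 reduction, two sites | Williams crossover test, named and powered |
| 10.3 | Effect of pollutant or source concentration | Mixed models, terms written out |
| 14.3 | Responses by site classification | None given |

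The site comparison is named and powered, but the only section that sets out models does not include it. The models in 10.3 match Objective 3.

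**2. Reproducing the 91.54%**

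Inputs from 10.1: difference 4.69, SD 6.4, n = 30, six sequences, alpha 0.05. Readings assumed here: 6.4 is the SD of the paired difference; an inequality test is two-sided; degrees of freedom are 30 − 6 = 24.

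- Standard error = 6.4/√30 = 1.168.
- Noncentrality = 4.69/1.168 = 4.014.
- Power = P(T > critical value), where T is noncentral t with 24 df and noncentrality 4.014.

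| Two-sided alpha per pair | Critical t (24 df) | Power |
|---|---|---|
| 0.05 | 2.064 | 97.05% |
| 0.05/3 = 0.0167 | 2.574 | 91.54% |

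Solving for the alpha that gives 91.54% with 24 df returns 0.01666.

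**3. Do other readings recover 91.54% at 0.05?**

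- Normal approximation at 0.05: 98.00%.
- t with 29 df at 0.05: 97.24%.
- 6.4 as a per-site SD with uncorrelated sites (difference SD 6.4 × √2 = 9.05): 77.7% with 24 df, 78.3% with 29 df.
- To keep 0.05 with 24 df, the SD of the difference would have to be 7.39.
- Normal approximation at 0.05/6: 91.55%, which is close to the printed figure. The match at 0.05/3 is therefore strong evidence but not proof.

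**4. Power at the planned recruitment**

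Completers: 48 × 0.70 = 33.6, taken as 33; 48 × 0.80 = 38.4, taken as 38. Paired test, alpha 0.0167, n − 6 df, participants independent:

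- n = 33: noncentrality 4.210, power 94.4%.
- n = 38: noncentrality 4.517, power 97.2%.

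**5. How far this depends on independence**

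Section 9.3 has a participant joined by up to three others at a site visit, and 10.1 forms groups of four. Participants can therefore share a site-day. The protocol gives no within-session correlation, so the values here are assumptions. With 33 completers in 12 groups, the mean group size is 33/12 = 2.75, and the variance inflates by 1 + 1.75 × ICC:

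| Assumed ICC of the paired difference | Inflation | Power, n = 33, alpha 0.0167 |
|---|---|---|
| 0 | 1.000 | 94.4% |
| 0.05 | 1.088 | 92% |
| 0.10 | 1.175 | 90% |
| 0.20 | 1.350 | 85% |

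**The case against.** The strongest reply is that the protocol does plan a site analysis. Section 9.7 says that the Williams test will be used, 10.1 powers it, and 14.3 lists site classification as one of the ways responses will be examined. Section 10.3 never claims to be the only or the primary analysis, and its covariate lists are open-ended. Two analyses described in two places may be incomplete drafting rather than contradiction, and a statistical analysis plan may fill in the model.

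Much of this stands. A reader might infer that no site comparison is intended, or that Objective 1 will go untested. The documents do not support that, because 9.7, 10.1 and 14.3 all point to a site comparison. The absence of a period term would, by itself, be a detail for the analysis plan; with six balanced sequences and complete data, leaving it out does not bias the site contrast. What remains is narrower. The protocol writes out models for a secondary objective in some detail and gives none for the comparison that it randomises and powers.

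On power, the reply is that 91.54% is correct if 0.05 is the level across three pairs, which is a normal use of the phrase. That is fair, and a reader should not infer a miscalculation or too small a sample. The remaining defect is that 10.1 does not say so, and that the meaning of 6.4 must be guessed.

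**Conclusion.** The point holds as a mismatch between sections and an unstated alpha. It does not show a missing objective or a failed sample size.

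- **Model.** The powered between-site FEV1 contrast is not carried into 10.3, whose exposure terms are non-randomised concentrations. This rests on the text alone.
- **Alpha.** The printed power is 5.5 points below what a two-sided 0.05 per comparison gives (97.05% − 91.54%), and it matches 0.0167 per pair. This assumes that 6.4 is the SD of the paired difference, a two-sided test and 24 df. The split over three pairs is an inference for the sponsor to confirm.
- **Sample size.** The recalculation gives no reason to change the target of 48. However, the 94.4% to 97.2% at 33 to 38 completers is conditional on independent participants. It should not be read as an unconditional assurance, because shared sessions would reduce it by an amount that the protocol does not allow one to fix.

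**What to change.** **Section 10.3.** Name as the primary analysis for Objective 1 a mixed model of FEV1 change with site and period as fixed effects and participant as a random effect. Allow for the shared site-day session, for example with a session random effect. Report the three site differences with confidence intervals, under the same error control as in 10.1. Keep the concentration models and assign them to Objective 3.

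**Section 10.1.** Have the sponsor confirm and state (a) whether 0.05 is the family-wise level, with 0.0167 per pair, and (b) that 6.4 is the SD of the paired difference. If 0.05 per pair was meant, restate the power as about 97%. State that the power assumes independence between participants who attend together.

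**Cost.** Rewording of two sections and slightly more analysis work; no new data and no change in recruitment. If session correlation is present, the confidence intervals for the site differences will be somewhat wider.

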5.2. Rationale

In an effort to reduce air pollution a number of government and industrial policies have been developed to increase sales of electric and hybrid cars. Electric and hybrid vehicles produce less air pollution from exhausts but due to their increased weight, they increase air pollution from tyre and road wear with an uncertain contribution from brake wear. Air pollution particles arising from tyre and brake wear, as well as resuspension of road dust, now represent a greater proportion of roadside PM by mass than direct tailpipe emissions. These Non-Tailpipe Emissions (NTE) remain unregulated, and their health impacts under explored, particularly in vulnerable groups.

Previous work by our team⁶⁻¹² demonstrated the feasibility of a quasi-experimental human real-world exposures using a crossover design for disentangling relative contributions of pollutant metrics on acute cardiopulmonary endpoints in healthy adults. Whilst this work showed the key role played by primary gaseous and particulate emissions, the study focused on responses in healthy adults and did not

examine biological pathways likely to lead to symptom exacerbation in vulnerable asthmatic populations. The study did examine a range of metals such as Fe, Cu, Ni and V, reflecting their capacity to cause oxidative stress, but did not explicitly relate these to NTEs, nor employ them for detailed source apportionment.

Our previous work has consistently shown that coarse mode PM is more effective at driving dendritic cell maturation and T-cell activation, than PM_{2.5} samples from urban background and roadside sites, or freshly collected diesel tailpipe PM. Given that such changes were observed in vitro this provides suitable rationale that health changes may be observed in asthmatic participants as people living with asthma are uniquely sensitive to the impacts of air pollution.

To date, no research has explored whether real-world NTE are causally related to worsening of asthma. Therefore, we aim to explore the hypothesis that clinically important adverse acute asthmatic responses are driven by non-tailpipe components within coarse mode PM.

6. Study objectives

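### Section 10.3 lets single-source significance decide which pollution sources enter an undefined joint model and compares sources partly on significance, which is a weak basis for attributing effects to non-tailpipe sources

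*Protocol*

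**What the plan says.** Protocol section 10.3 starts with one model per source type. It continues: "then we can decide how to develop a model with all of the significant source types". The sources are tailpipe, represented by black carbon and organic aerosol, and non-tailpipe, split into brake wear and combined tyre and road wear. On comparing them, 10.3 says: "The effects of different pollutants will be compared based upon statistical significance and the effect size for selected exposure contrasts".

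Two other sentences in 10.3 bear on this. One is "Levels (eg. Integrated average concentration) of each source (tailpipe/non-tailpipe) will be included in the model", which does not say whether the sources enter together or one at a time. The other is "Two pollutant models will be specified as well to evaluate which pollutant has the strongest association with a certain health endpoint".

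Section 10.2 plans graphs "to get insight in the correlation between different exposure variables". The protocol gives no correlation values, no fixed joint model and no rule for collinear sources.

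The hypothesis in section 5.2 is that "clinically important adverse acute asthmatic responses are driven by non-tailpipe components within coarse mode PM". Objective 3 (section 6.2) relates the non-tailpipe source fractions to the responses.

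**The concern.** Objective 3 and the hypothesis need the effect of each source adjusted for the others. A single-source model does not provide that: where sources rise and fall together, a source with no effect takes on part of its neighbour's effect. Its estimated effect size is biased in the same way as its p-value, so adding effect size as a second criterion does not help at that stage.

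The screen adds two problems. A source with a real effect that misses significance is left out, and so is no longer adjusted for. Intervals from a model chosen after seeing the results can also lose their stated coverage.

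Separately, one source being significant while another is not does not test whether the two differ.

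At stake is whether a tailpipe effect could be credited to brake or tyre wear, or the reverse.

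**Working it through.** **The plan's own figure.** The only power figure is 91.54% (section 10.1: difference 4.69, SD 6.4, 30 participants). SE = 6.4/√30 = 1.168 and 4.69/1.168 = 4.01. A noncentral t with 24 df and two-sided alpha 0.05/3 gives 0.9154, so the figure is reproduced. The division by 3 and the 24 df are inferred, not stated. The figure concerns a contrast between two sites; no power is given for separating sources.

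**Is correlation plausible?** Section 9.4 puts brake wear at White City at 85% of Marylebone Road, with 93,000 against 51,000 vehicles per day. The third site is urban background.
- Assume background is a fraction f of Marylebone Road, f = 0 to 0.5, for both brake wear and tailpipe.
- If tailpipe scales with vehicle count, at f = 0 the site means are brake (1, 0.85, 0) and tailpipe (51, 93, 0). Sum of cross-products 41.25, sums of squares 0.5817 and 4338, so r = 41.25/√(0.5817 × 4338) = 0.82. At f = 0.5, r = 0.57.
- If tailpipe is equal at the two roads, r = 0.96 to 0.99.

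These are site means under assumptions. Day-to-day variation within sites may lower the correlation.

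**Simulation settings.** One causal source and one or two null sources.
- Completers: 48 × 0.75 = 36, in 9 groups of 4, with 3 sessions each and exposure shared within a session.
- Residual SD per visit: 6.4/√2 = 4.5.
- Screen at 0.05 (10.3 states no threshold; 0.05 appears in 10.1).
- Causal effect of 1 or 2 points of FEV1 change per SD of exposure.
- Correlation ρ of 0.5 to 0.85, assumed.

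**Hand check of the single-source step.** The probability that a null source passes is about Φ(δρ − 1.96), with δ = effect × √(2 × 36)/4.5. This gives δ = 3.77 at 2 points and 1.89 at 1 point.

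| Effect | ρ | Formula | Simulation |
|---|---|---|---|
| 2 | 0.5 | Φ(−0.07) = 47% | 40-43% |
| 2 | 0.7 | Φ(0.68) = 75% | about 65% |
| 2 | 0.85 | Φ(1.25) = 89% | about 83% |
| 1 | 0.5 | Φ(−1.02) = 15% | about 17% (low end) |
| 1 | 0.85 | Φ(−0.36) = 36% | about 34% (high end) |

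The formula runs high at 2 points because it ignores the chance variation in exposure over a small number of shared sessions. With all sources in one model, the null source is significant in about 5% of studies.

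**What happens after the screen.**
- A given null source is significant in the final screened model in about 3-6% of all studies.
- Among studies where the null source passed the screen, its final 95% CI covers zero in about 73-88% at 1 point per SD and in about 93-96% at 2 points.
- Part of the loss at 1 point arises when the causal source, with only about 45% power, fails the screen. If the null source is then the only one left, the final model is the single-source fit that already excluded zero.

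**Ranking by p-value.** At 1 point per SD, a null source has the smaller p-value in about 22-34% of studies with one null source and 32-47% with two. In the joint model such reversals are as frequent or more so; with exactly two sources the order is the same in both models.

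**The case against.** The strongest reply is that 10.3 does not stop at the single-source fits. It goes on to a joint model and to two-pollutant models. The latter are not said to depend on the screen, and they bring a null source back to about 5% when the causal source is the other term. 10.3 also says that the level of each source will be in the model, and it adds effect size to significance when comparing sources. The three sites were chosen to contrast brake and tyre wear. Source attribution is a secondary objective; the primary one compares sites. The details of the joint model may be in a statistical analysis plan that is not at hand.

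Much of this stands. A reader might infer that tailpipe and non-tailpipe effects will routinely be confused, or that 40-83% of studies would end by naming the wrong source. The documents do not support that: those percentages describe an intermediate step, the later models hold the overall rate near 3-6%, and every correlation is assumed. Nor can p-value reversals be blamed on the screen, since a joint model shows them too; they reflect low power and argue against ranking by significance in any model.

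What does not stand is that the later models settle the matter. The two-pollutant models are there to find the strongest association, which is again a ranking, and with three or four source terms a pair leaves others unadjusted. The sentence on source levels does not say that they enter jointly, and it sits beside the significance rule. That rule is stated in the protocol, so an analysis plan that follows it inherits it.

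**Conclusion.** The concern holds in a limited form. Section 10.3 ties entry to the joint model to single-source significance, leaves that model's form open until those results are known, and uses significance to compare sources. With correlations of 0.5 to 0.85, single-source effect sizes and p-values cannot attribute an effect to non-tailpipe sources: a null source passes alone in about 40-83% of studies at 2 points per SD and 17-34% at 1 point, against about 5% jointly.

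Damage to the final model is limited to weak effects (coverage about 73-88% at 1 point per SD); at 2 points per SD coverage is near nominal. The risk is therefore misattribution in single-source comparisons and when effects are weak, not routine confusion.

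The sizes rest on assumed correlations, effect sizes, completers and screening threshold. The sample size and the stated power for the site contrast are unaffected. The wording should be changed before the data are seen.

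**What to change.** In section 10.3:
- Make one pre-specified mixed model, holding all three apportioned source groups (tailpipe, brake wear, tyre and road wear) whatever their single-source p-values, the basis for source attribution under Objective 3.
- Report each coefficient per interquartile range, or another contrast fixed in advance, with its CI.
- Compare sources by the CI of the difference between their coefficients. Remove selection and comparison by statistical significance.
- Report the correlations between sources and the variance inflation, and state in advance that sources too collinear to separate will be reported as not separable.
- Keep the single-source and two-pollutant models as descriptive.

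This needs only a change of wording, but it has a statistical price. For a source with 90% power alone, power in the joint model is about Φ(3.24 × √(1 − ρ²) − 1.96), and variance inflation is 1/(1 − ρ²):

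| ρ | Variance inflation | Power |
|---|---|---|
| 0.5 | 1.3 | 80% |
| 0.7 | 2.0 | 64% |
| 0.8 | 2.8 | 49% |
| 0.9 | 5.3 | 29% |

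The wider intervals show how little the data can say about each source separately. The collinearity rule is needed so that a wide interval is not read as absence of effect.
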